5.7.3 Premature Termination or Suspension of Study

This study may be temporarily suspended or prematurely terminated if there is sufficient reasonable cause. Written notification, documenting the reason for study suspension or termination, will be provided by the suspending or terminating party to the PI, appropriate funding agency, and New York University IRB. If the study is prematurely terminated or suspended, the PI will promptly inform the IRB and will provide the reason(s) for the termination or suspension.

Circumstances that may warrant termination or suspension include, but are not limited to:

- Determination of unexpected, significant, or unacceptable risk to participants
- Demonstration of efficacy that would warrant stopping
- Insufficient compliance to protocol requirements
- Data that are not sufficiently complete and/or evaluable
- Determination of futility

Study may resume once concerns about safety, protocol compliance, data quality are addressed and satisfy the sponsor and/or IRB.

6 Behavioral/Social Intervention

6.1 Study Behavioral or Social Intervention(s) Description

Sleep Intervention Arm: The sleep intervention is based on Cognitive Behavioral Therapy for Insomnia (CBT-I). Participants may not require the initial sleep restriction that characterizes the first step of CBT-I if their sleep efficiency is > 90%. However, the sleep intervention will employ CBT-I's gradual approach for increasing sleep time and applying it to short sleepers. The 8-week intervention period of gradually increasing sleep duration by advancing bedtimes 15 minutes per week (or 1 hour per month) will provide the time needed to increase sleep duration in habitual 5 hour sleepers to the recommended 7 to 8 hour sleep duration. Like CBT-I, the sleep intervention extends sleep duration based on sleep efficiency (the proportion of time spent sleeping during a sleep episode). Bed times and wake times will be prescribed each week for each participant and allow for gradual increases in sleep opportunity. Bedtimes will be set 15 minutes earlier each week provided sleep efficiency remains >90%. Earlier bedtimes will extend sleep duration by increasing the opportunity for sleep. Wake times will not be changed because wake times are often determined by external demands, such as work schedules. Participants in the sleep intervention arm will receive generic nutrition, physical activity, and psycho-social self-management recommendations as per the ADA lifestyle management guidelines for adults with prediabetes.

Control Arm: The control arm will receive a time and attention matched intervention that is based on the ADA lifestyle management guidelines for adults with prediabetes. Content covered will include nutrition therapy, physical activity, and psycho-social education. Participants in the control arm will receive generic sleep hygiene recommendations.

6.1.1 Administration of Intervention

This intervention will be delivered by a trained study team member. It will consist of 8 weekly sessions. Sessions 1-8 for the intervention and control arms will consist of 45-60 minute HIPPA compliant Zoom videoconference or phone call sessions. An optional final study visit (30-minute HIPPA compliant Zoom videoconference or phone call session) will be scheduled for interested participants after all end of treatment measurements are completed and wearable technology returned (wrist accelerometer and continuous glucose monitor)

CONFIDENTIAL

This material is the property of the NYU School of Medicine and NYU Langone Health. Do not disclose or use except as authorized in writing by the study sponsor
Behavioral Intervention Template Version: 11 January 2019

At this final visit, a study team will review the participant's baseline and end of treatment continuous glucose monitoring reports, wrist accelerometer, weight measurements, and ASA24 reports with participants.

If participants do not have access to a laptop, computer, tablet, or telephone for these sessions several alternatives will be offered to ensure that low income individuals are not excluded. A tablet will be offered to participants as needed for the duration of the intervention. Participants will return the tablets at their second CTSI visit. Alternatively, sessions may take place in-person and participants will be compensated for their travel to and from these sessions.

6.1.2 Procedures for Training Interventionalists and Monitoring Intervention Fidelity

The PI and trained study team members will be responsible for administering the intervention. We will use recommendations of the Treatment Fidelity Workgroup of the NIH Behavior Change Consortium⁹⁸ to enhance the intervention fidelity. The treatment fidelity plan includes audiotaping each session and reviewing content against an a priori performance checklist to ensure consistency in the intervention delivery. Participants and staff will be told not to state the participant's name or any identifying information during these sessions to ensure participant confidentiality with respect to the stored audio recordings.

Treatment fidelity will be monitored by the PI and research team. Barriers to implementing the intervention will be identified and resolved.

6.1.3 Assessment of Subject Compliance with Study Intervention

The study team will track participant compliance by monitoring daily sleep diary completion, baseline and end of treatment survey completion, and weekly intervention session attendance. Retention rates for both arms will be monitored by the study team. Daily texts or email reminders will be sent to participants to remind them to complete the sleep diaries each evening as needed.

7 Study Procedures and Schedule

7.1 Study Procedures/Evaluations

7.1.1 Study Specific Procedures

Participants meeting the telephone screen eligibility criteria will be invited to the CTSI. CTSI visit 1 will be scheduled within 4 weeks of the telephone screen. At the CTSI visit 1, participants will provide written informed consent prior to the study specific procedures listed below. All surveys at the CTSI will be completed using REDCap.

- Medical history will be obtained by completing specific surveys at the CTSI visit 1. Surveys will include: Alcohol Use Disorders Identification Test (AUDIT), ARES, Insomnia Severity Index, selected questions from the Sleep Disorder Symptom Checklist -25 , the NINR BRICS with race clarifying questions, Patient Health Questionnaire (PHQ-9), Primary care provider contact information, and a targeted health survey. Prediabetes (HbA1c \geq 5.7% and $<$ 6.5%) will be confirmed from the NYULH medical records (for NYULH participants) or from a HbA1c point of care fingerstick test (for non-NYULH participants).
- Medication history will be obtained by completing specific surveys at the CTSI visit 1. Surveys will include self-reported prescription and over-the counter medications. Specific permitted and prohibited medications will also be queried. Prohibited medications include prescribed medications for T2DM with the exception of Metformin and chronic use of prescribed or over the counter sleep medications (greater than or equal to three times per week).
- Physical examination performed at the CTSI visit will be targeted and include a measured height, waist, and weight, neck circumference, and blood pressure.

CONFIDENTIAL

This material is the property of the NYU School of Medicine and NYU Langone Health. Do not disclose or use except as authorized in writing by the study sponsor
Behavioral Intervention Template Version: 11 January 2019

- Radiographic or other imaging assessments. Not applicable.
- Biological specimen collection and laboratory evaluations. Participants who do not have the results of a HbA1c within the previous 3 months of the CTSI visit 1 will have a Hemoglobin A1c point of care fingerstick to confirm high risk prediabetes. Participants may also be offered the option to provide a blood sample that will be de-identified for future analysis of biomarkers for metabolic disorders, sleep or circadian health, or other health conditions See Section 7.2. All blood draws will take place during the CTSI visit 1.
- A discussion of the results of any study specific procedures that will be provided to the participant include results from the 1) ARES indicating high risk for sleep apnea (≥ 6), 2) PHQ-9 indicating moderate/severe depression (>15), or 3) HbA1c test results from the CTSI visit 1 in the T2DM range ($\geq 6.5\%$). Participants with a high-risk ARES score or previously diagnosed and currently treated OSA will complete 1 night of pulse oximetry measurements during the 2-week at home baseline assessment to confirm absence of moderate to severe OSA or the effectiveness of the current OSA treatment regime (AHI ≤ 10). Participants not previously diagnosed and treating OSA will be provided with a list of sleep clinics and encouraged to follow up with a provider for further testing and evaluation. Participants with ineffectively treated OSA will be encouraged to follow up with their health care provider managing their OSA. Participants responding “several days”, “more than half the days” or “nearly every day” to the PHQ-9 question: “Over the past 2 weeks, how often have you been bothered by any of the following problems?....Thoughts that you would be better off dead or of hurting yourself” will be screened further at the CTSI visit 1 by the project coordinator as per the Depression Safety and Referral Protocol.
- Participants with HbA1c point of care fingerstick test results from in the T2DM range of $\geq 6.5\%$ will be provided their test results as outlined in the protocol.
- Counseling procedures. Not applicable.
- Assessment of study intervention adherence will be monitored by the completion of daily sleep diaries and by the attendance at the weekly intervention sessions.
- Administration of questionnaires or other instruments for participant outcomes, include Sleep Diaries (daily); Epworth Sleepiness Scale (weekly); and SRM-5 (daily for the 2-week baseline and 2-week end of treatment study period), ASA24 hour dietary recall (baseline and end of treatment); Composite Scale of Morningness (baseline); International Physical Activity Questionnaire (baseline and end of treatment); Pittsburgh Sleep Quality Index (baseline and end of treatment); PROMIS-Depression 6a (baseline and end of treatment); and Sleep Environment Survey (baseline) will be administered through the Assessment Center Application Programming Interface in REDCap (Research Electronic Data Capture) and during CTSI visit 2 (end of treatment surveys).

Wearable sensor technology assessments will be as follows: pulse oximeter (baseline for 1 night, as needed); Wrist accelerometer (baseline and end of treatment 24/7 for 14 nights); Continuous glucose monitor (baseline and end of treatment 24/7 for 7 days).

7.1.2 Standard of Care Study Procedures

All participants will receive lifestyle management information for the prevention of T2DM focused on nutrition and physical activity during the intervention as per the 2019 ADA Standards of Care⁹⁹.

7.2 Laboratory Procedures/Evaluations

7.2.1 Clinical Laboratory Evaluations

Participants *without* evidence of a HbA1c within the previous 3 months or from outside the NYULH system will have a HbA1c point of care fingerstick test after enrollment (5 μ L). This approach is consistent with other studies examining the relationship between sleep and metabolic outcomes whereby most recent bloodwork from subject’s medical records were used⁶⁹. Participants recruited from outside the NYULH system will have a HbA1c point of care fingerstick test after enrollment. Participants providing consent for the optional blood draw may have the blood specimen collected by peripheral vein venipuncture at the NYULH CTSI Clinical Research Center (CRC) at Bellevue Hospital C/D Building, 4th floor by the Clinical Research Coordinators. The estimated total volume of blood drawn is 20 ml.

CONFIDENTIAL

This material is the property of the NYU School of Medicine and NYU Langone Health. Do not disclose or use except as authorized in writing by the study sponsor

Behavioral Intervention Template Version: 11 January 2019

Table 1: Blood collection			
	Volume required	Specimen type	Collection tube
Hemoglobin A1c point of care fingerstick	5 μ L	Whole blood	Not applicable
Optional Blood draw	20 ml	Whole blood	EDTA

7.2.2 Other Assays or Procedures

Not applicable.

7.2.3 Specimen Preparation, Handling, and Storage

All vacutainer tubes for the optional blood draw will be labeled with participants' unique study ID without PHI.

7.2.4 Specimen Shipment

Not applicable.

7.3 Study Schedule

7.3.1 Screening

Telephone Screening Visit (Day -30 to -1)

- Obtain verbal consent from potential participant to continue with the scripted telephone screen.
- Provide participants with general information about the study as per the scripted telephone screen.
- If interested, continue with the scripted telephone screen to determine potential eligibility for CTSI visit 1.
- If eligible based on telephone screen, schedule the CTSI visit 1 within 30 days of the telephone screening date.

7.3.2 Enrollment/Baseline

Enrollment/Baseline CTSI Visit 1 (Visit 1, Day 0)

- Obtain written informed consent and written audio consent of the potential participant verified by signature on study informed consent form.
- Verify inclusion/exclusion criteria.
- Review medical history to determine eligibility based on inclusion/exclusion criteria (prediabetes diagnosis, most recent HbA1c \geq 5.7% and $<$ 6.5%, no diagnosis of current or previous bipolar disorder).
- Obtain demographic information, medical history, medication history, and alcohol use history.
- Record vital signs, results of examinations, other assessments.
- HbA1c point of care fingerstick (if needed) and blood draw for future analyses (optional).
- Provide eligible participants with instructions for the at-home assessments with wrist accelerometry, continuous glucose monitoring, pulse oximetry (if needed), and baseline surveys via REDCap including daily sleep diaries.

CONFIDENTIAL

This material is the property of the NYU School of Medicine and NYU Langone Health. Do not disclose or use except as authorized in writing by the study sponsor
Behavioral Intervention Template Version: 11 January 2019

7.3.3 Intermediate Visits

7.3.3.1 At-home visits

Week 1 (Days 1 - 7)

- Record adverse events as reported by participant or observed by investigator.
- Participant will wear the continuous glucose monitor for 7 days 24/7. Return the continuous glucose monitor to the study team in the prepaid package after day 14.
- If needed, participant will wear the pulse oximeter for 1 night. Return the pulse oximeter to the study team in the prepaid package after 1 night of wear time.
- Record results of continuous glucose monitor and pulse oximeter.
- Participant will wear wrist accelerometer (24/7).
- Complete Sleep Diaries (daily), SRM-5 (daily), and Epworth Sleepiness Scale (day 6)
- Complete baseline surveys: ASA24 hour dietary recall; Composite Scale of Morningness; International Physical Activity Questionnaire; Pittsburgh Sleep Quality Index; PROMIS-Depression 6a; Sleep Environment Survey.
- Record participant's adherence to intervention program.

Week 2 (Days 8 - 14)

- Record adverse events as reported by participant or observed by investigator.
- Record results of wrist accelerometer.
- Complete Sleep Diaries (daily), SRM-5 (daily) and Epworth Sleepiness Scale (day 13).
- Record participant's adherence to intervention program.

Week 3 (Days 15-21)

- Participant to ship wrist accelerometer back to the study team in the prepaid package after 14 nights of wear time (day 15).
- Record adverse events as reported by participant or observed by investigator.
- Determine eligibility for intervention based on wrist accelerometry and pulse oximetry data.
- Randomize eligible participants to sleep intervention or control arm.
- Notify participant of eligibility and arrange for weekly videoconference intervention sessions.

Weeks 4-11 (Days 22 – 77)

- Record adverse events as reported by participant or observed by investigator.
- Record results of daily Sleep Diary and weekly Epworth Sleepiness Scale results.
- Administer the study intervention to the participant in accordance with the intervention manual for the sleep intervention arm or the control arm.
- Record participant's adherence to intervention program.

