Actigraphy monitoring may lead to local discomfort including skin irritation beneath the band. Wearing the accelerometer may also be inconvenient or uncomfortable. Participants will be free to remove the actigraph as needed. We will request that they note this in their sleep diary.

Inserting the *continuous glucose monitor* sensor into the back of a participant's upper arm may cause redness, pain, bruising, bleeding, or infection at the insertion site. Wearing the sensor may also be inconvenient, uncomfortable, and cause other more serious skin problems. The sensor is water-resistant and can be worn for bathing, showering or swimming. However, sensors cannot be taken in water deeper than 3 feet or for longer than 30 minutes. Sensors must be removed prior to MRI, CT scan, X-ray or diathermy treatment. Some airport full-body scanners include x-ray or millimeter radio-wave and will require the sensor to be removed if participants choose to go through these full body scanners. Also, sensors may lose adherence and fall off requiring the study team to insert another continuous glucose monitor sensor. Broken sensor probes are considered a minor risk and, although rare, are possible. To protect against a

CONFIDENTIAL

This material is the property of the NYU School of Medicine and NYU Langone Health. Do not disclose or use except as authorized in writing by the study sponsor

Behavioral Intervention Template Version: 11 January 2019

broken sensor probe under the skin, a trained study team member will insert sensors for participants and participants will be required to verify that sensors have been removed at the end to the 7-day period.

Sleep interventions. Extending sleep may be associated with sleep complaints as well as insomnia. These risks will be protected against by personalizing sleep intervention strategies designed from the participant's habitual sleep patterns and based on an existing sleep intervention protocol. If sleep is restricted due to low sleep efficiency, participants may experience sleepiness. To protect against excessive sleepiness, participants will be monitored weekly with the Excessive Sleepiness Survey. Strategies for managing sleepiness and modifications to the sleep intervention (e.g. napping, flexible sleep schedules) will be implemented.

- *Rationale for the necessity of exposing human participants to such risks*

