5.5 Duration of Study Participation

Study participants' participation will involve a 3-4 week baseline phase that will include the CTSI visit 1, a 2 week at-home baseline assessment for sleep and glycemic control, using accelerometers (14 nights), continuous glucose monitors (7 days), and pulse oximetry (1 night, if needed). These 2 weeks will be followed by a 1-week review of the at-home data by the PI to assess continued eligibility (e.g., objectively confirmed short sleep). The at-home baseline assessment will be followed by the 8-week intervention. After the 8-week intervention, participants will return to the CTSI for the wrist accelerometer and continuous glucose monitor for the 2-week at-home end of treatment assessment. Thus, participants can anticipate involvement in the study for approximately a 15 week period.

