7.3.6 Unscheduled Visit

If a participant needs an unscheduled visit for replacing the continuous glucose monitor, this visit will be arranged by the project coordinator and documented in REDCap.

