### **1.3.2 Analysis of the Primary Efficacy Endpoint(s)**

A multivariable Linear regression model was used to assess the effect of the sleep intervention with the subject specific change in the percent time glucose is  $\geq 140$  (Time above target) from baseline as the continuous outcome variable and intervention arm (0=Control Intervention [CI], 1=Sleep Intervention [SI]) as a dichotomous predictor. Effect sizes were presented as beta coefficients and associated 95% confidence intervals, equal to the expected difference between the SI and CI. Important covariates that will be controlled for in these analyses include demographic characteristics including age (continuous), sex (female/male), and race (Asian, Black, White, Other). Statistical significance was determined with a  $p$ -value  $< 0.05$  using a two-tailed test for significance. Normality was assessed using a skewness cutoff of  $\pm 2$ , following established guidelines.

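### The week-3 check before randomisation does not require a usable baseline CGM record, although the primary outcome is the change from that baseline

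*Protocol*

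**What the plan says.** - **Week-3 decision.** Protocol 7.3.3.1 (Week 3) has staff "Determine eligibility for intervention based on wrist accelerometry and pulse oximetry data"; the next step is "Randomize eligible participants to sleep intervention or control arm".
- **Other description of the same week.** Protocol 5.5 lists accelerometer, CGM and oximeter as the at-home baseline and follows it with a "1-week review of the at-home data by the PI to assess continued eligibility (e.g., objectively confirmed short sleep").
- **Eligibility.** Nothing in Protocol 5.1 or 5.2 refers to a CGM record. Neither document sets a minimum wear time or number of valid readings.
- **Device timing.** The sensor is worn on days 1–7, and week 1 of 7.3.3.1 says "Return the continuous glucose monitor to the study team in the prepaid package after day 14". The accelerometer is shipped on day 15.
- **Sensor loss.** Protocol 2.3.1 warns that "sensors may lose adherence and fall off requiring the study team to insert another continuous glucose monitor sensor", and also has participants confirm removal when the 7 days are over. Section 7.3.6 provides for replacement: "If a participant needs an unscheduled visit for replacing the continuous glucose monitor, this visit will be arranged by the project coordinator".
- **Analysis.** SAP 1.3.2, like Protocol 10.4.2, models the change "from baseline as the continuous outcome variable and intervention arm". The primary set is everyone randomised (Protocol 10.3, SAP 1.2).
- **Missing baseline.** Protocol 10.4.1 mentions imputation only in connection with non-normal variables. SAP 1.3.1 says only that the data were examined for anomalies, among them nonrandom missingness. Neither states what happens when the baseline is absent.

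**The concern.** A change score needs both ends. The instrument that supplies the baseline end is the one missing from the week-3 step, so a site following 7.3.3.1 to the letter can randomise a participant whose baseline CGM is unusable. That participant belongs to the intention-to-treat set but cannot enter the planned regression, however well they complete the trial. Their baseline cannot be measured again once treatment has begun.

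At stake are the precision of the primary comparison and the match between the stated analysis set and the set the model can use. The 20% allowance in Protocol 10.5 is framed around losses in the 8 treatment weeks, so it does not name this source. Unlike later drop-out, this loss can be prevented, because the participant has not yet been randomised when it occurs.

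**Working it through.** **1. The plan's own figures (Protocol 10.5).**

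- Effect: 69.2 / 57.7 = 1.199 SD; half of the plan's 1.2 is 0.6 SD.
- Power for n per arm, two-sided alpha 0.05, from the noncentral t with 2n − 2 degrees of freedom and noncentrality 0.6 × √(n/2).
- n = 73 gives 94.96% and n = 74 gives 95.2%, so 74 per arm is reproduced. The planned 75 gives 95.5%.
- Inflation: 75 / 0.80 = 93.75, rounded up to 94 per arm, 188 in total. Retained: 188 × 0.80 = 150.4, about 150.

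The stated sample size is correct on its own terms.

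**2. Adding a missing-baseline rate m.** The documents give no value; 3–10% is an assumption, meant as the rate left after any replacement visits. Losses are taken as independent: analysable total = 188 × 0.80 × (1 − m), and per arm = 75.2 × (1 − m), rounded down.

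| m | No baseline, 188 × m | Analysable total | Per arm | Power at 0.6 SD |
|---|---|---|---|---|
| 0 | 0 | 150.4 | 75 | 95.5% |
| 3% | 5.6 | 145.9 | 72 | 94.7% |
| 5% | 9.4 | 142.9 | 71 | 94.4% |
| 10% | 18.8 | 135.4 | 67 | 93.2% |

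If the two losses add instead, 10% gives 94 × (0.80 − 0.10) = 65.8, so 65 per arm and 92.4% power. Keeping 75 analysable per arm without the check would mean randomising 75 / (0.80 × (1 − m)) per arm: 97 at 3%, 99 at 5% and 105 at 10%, against 94 planned.

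**3. Does a repeat wear fit?** In 7.3.3.1 the intervention starts on day 22, so a repeat must be worn, returned and read by day 21.

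- Sensor returned after day 7: 21 − 7 − 7 = 7 days for two mail-backs, two downloads and one insertion visit. Possible, but tight.
- Sensor returned after day 14, as now: 21 − 14 − 7 = 0 days. It does not fit.

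Protocol 5.5 allows a baseline phase of 3–4 weeks. Counted from day 1, a fourth week adds 7 days to each figure.

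**The case against.** The best counter-argument is Protocol 5.5. Its list of at-home measures includes CGM, the review covers those data, and short sleep is offered only as an example. Protocol 10.6.1 also places randomisation after baseline data collection, and 5.6 aims for 188 evaluable participants. Staff may well look at the CGM record before randomising. What survives is narrower: the 5.5 review serves eligibility, CGM adequacy is not an eligibility criterion, and the operative step in 7.3.3.1 names two other devices. The two sections are not aligned.

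Some stronger readings are tempting, and the documents do not support them:

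- *That CGM data necessarily arrive too late.* The sensor is due back after day 14 and the accelerometer ships on day 15. If one can be read in time for week 3, so can the other.
- *That a failed sensor comes to light only after the baseline weeks.* The removal check in 2.3.1 falls at the end of the 7-day wear, and Attachment A marks a compliance check in weeks 1 and 2. A sensor that falls off is likely to be noticed; silent failure of the device is the clearer risk.
- *That every early failure means no outcome.* A partial record can still yield a percentage. With no minimum-data rule, the plan does not say whether that value counts.
- *That the comparison would be biased.* A failure before randomisation should be unrelated to arm.

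**Conclusion.** The point holds as a gap in the written procedure. Nothing in 7.3.3.1 or the eligibility criteria makes a usable baseline CGM record a condition of randomisation, and the primary analysis depends on one. Section 5.5 softens this but does not close it.

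The consequence is modest: at an assumed 3–10%, about 6–19 of 188 without a change score, about 146–135 analysable instead of 150, and power of about 93–95% instead of 95.5%. These figures rest on the assumed rate, on the plan's 0.6 SD and 20% later loss, and on a complete-case change-score analysis. They overstate the loss if partial records are accepted. A reader might infer that the trial is underpowered or its comparison biased; neither follows. The case for acting is that the loss falls on the primary endpoint and is cheap to prevent.

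**What to change.** 1. **Protocol 7.3.3.1, Week 3:** add a usable baseline CGM record to the conditions for randomisation, and define usable by a stated minimum of valid data. Without a definition, staff cannot apply the check.
2. **Protocol 7.3.3.1, Week 1:** have the sensor returned after the 7-day wear. At the latest, download it together with the accelerometer, before randomising.
3. **Unusable record:** use the replacement visit in 7.3.6 to repeat the 7-day wear before randomisation.
4. **Protocol 5.5:** align the description of the review with the amended week-3 step.

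The cost is a short amendment, a mail-back separate from the accelerometer's if the sensor comes back early, and a repeat sensor and visit for the few affected. Those few face a delay of about a week or somewhat more, which may not fit before day 22, so the amendment should say that their start may move.

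Much of the SAP is in the past tense. If enrolment has already closed, the remaining action is to report how many were randomised without usable baseline CGM and to state in the SAP how they are handled.
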